## **8. SUMMARY OF CHANGES FROM PROTOCOL-SPECIFIED ANALYSES**

No changes are planned.

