2.3 Exploratory Objectives

- To assess the prognostic and predictive value of the expression of baseline immunohistochemistry (IHC) markers of interest (e.g. PD-1, PD-L1, PD-L2, NKG2D, KIR2DL1/2/3), and change in expression, for pathologic partial and complete tumor response (defined by cystectomy pathologic staging <pT2N0 and pT0N0, respectively), in patients treated with nivolumab and combination of nivolumab/lirilumab.
- To assess the prognostic and predictive value of peripheral blood mononuclear cell (PBMC) T-cell subset status (%CD4+ T-cells, %CD8+ T-cells, %T_{reg} T-cells, %Myeloid Derived Suppressor Cells, %Natural Killer cells, etc.) and change in status, as assessed by flow cytometry analysis, for pathologic partial and complete tumor response (defined by cystectomy pathologic staging <pT2N0 and pT0N0, respectively), in patients treated with nivolumab and combination of nivolumab/lirilumab.
- To compare CD8+ TIL density in post-treatment RC tissues in patients treated with nivolumab and combination of nivolumab/lirilumab.
- To assess the prognostic and predictive relationship between pre- and post- treatment TIL and NK-cell level and activation and pathologic partial and complete response (defined by cystectomy pathologic staging <pT2N0 and pT0N0, respectively) as well as two-year RFS, in patients treated with nivolumab and combination of nivolumab/lirilumab.
- To assess impact of prior BCG exposure on rates of pathologic partial and complete response (defined by cystectomy pathologic staging <pT2N0 and pT0N0, respectively) as well as two-year RFS, in patients treated with nivolumab and combination of nivolumab/lirilumab.

- To assess the prognostic and predictive relationship of tumor mutational load, neo-epitope burden, intrinsic molecular subtypes (basal vs. luminal), and T-cell clonality with pathologic partial and complete response (defined by cystectomy pathologic staging <pT2N0 and pT0N0, respectively) as well as two-year RFS, in patients treated with nivolumab and combination of nivolumab/lirilumab.
- To assess the prognostic and predictive relationship of pre- and post-treatment peripheral blood T-cell subsets, CD4+/CD8+ and CD4+/FOXP3+ ratios and plasma cytokine multiplex panels with pathologic partial and complete response (defined by cystectomy pathologic staging <pT2N0 and pT0N0, respectively) as well as two-year RFS, in patients treated with nivolumab and combination of nivolumab/lirilumab.

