13.2.3.1 Analytic Plan for Additional Secondary Objectives

1. The mean percent change of CD8+ TIL density from pre-treatment (TURBT) to post-treatment (radical cystectomy) samples in all 12 patients in Cohort 1 and all 24 patients in Cohort 2 will be calculated

and compared between the two cohorts using a Wilcoxon rank sum test.

2. The proportion of patients in each treatment cohort who do not get radical cystectomy specifically and directly related to treatment related AEs within 6 weeks of the completion of neoadjuvant treatment, will be reported along with exact binomial 90% confidence intervals for each cohort and compared between the two cohorts using Fisher's exact test.
3. The proportion of patients in each treatment cohort with pathologic complete response (CR) and pathologic partial response (PR) will be reported along with exact binomial 90% confidence intervals for each cohort.
4. Recurrence-free survival (defined as patients who are alive and without evidence of disease recurrence) from the time of registration will be estimated using Kaplan-Meier method for each treatment cohort and compared between the two cohorts using a log-rank test. One-year and two-year disease-free survival estimates and confidence intervals will be provided for each cohort.

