13.2.4.1 Analytic Plan for Exploratory Objectives

As a general strategy, marker levels in responders vs. non-responders will be compared by a t-test or Wilcoxon rank sum test as appropriate. In addition to evaluating expression on a continuous scale we will explore quantile values for each marker as potential thresholds to discretize the marker levels. The two-year RFS will then be compared between marker groups with a Fisher's exact test as well as via time-to-event analyses using standard methods for survival analysis. Changes in biomarker levels will be computed and compared between groups using a Wilcoxon rank sum test. Analyses of the predictive ability of markers will be accomplished via standard tests of treatment-by-marker interaction using the appropriate model for the endpoint of interest (logistic regression or proportional hazards regression). Pearson's correlation and the Wilcoxon signed rank test will be used to characterize the relationship between CD8+ TIL densities produced by various methods of assessment. The study is not powered for these analyses, however, so conclusions regarding the predictive ability of any given marker will be limited.

14. Laboratory and Pathology Correlative Studies

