## **2. INTRODUCTION**

### **2.1. Objective of the Statistical Analysis Plan**

This statistical analysis plan (SAP) describes the planned analysis of the safety and efficacy data from this study. A detailed description of the planned tables, figures and listings (TFLs) to be presented in the Clinical Study Report (CSR) is provided in the accompanying TFL template document.

The intent of this document is to provide guidance for the analysis of data related to safety and efficacy to describe any applicable statistical procedures. In general, the analyses come directly from the protocol, unless they have been modified by agreement between the Sponsor and Quality Data Services, Inc. (QDS). A limited amount of information concerning this study (e.g., objectives, study design) is summarized to help the reader interpret the accompanying TFL templates. That information is not a synopsis of the study and does not require review or approval because it is simply extracted from the protocol. Attached signatures indicate approval of the statistical analysis sections of the SAP, as well as accompanying TFL templates. These sections must be agreed upon prior to database lock. When the SAP and TFL templates are agreed upon and finalized, they will serve as the template for a portion of this study's CSR.

This SAP supersedes the statistical considerations identified in the protocol; where considerations are substantially different, they will be so identified. If additional analyses are required to supplement the planned analyses described in this SAP, they may be performed and will be identified in the appropriate section of the CSR. Any substantial deviations from this SAP will be agreed upon between the sponsor and QDS. Deviations from this SAP, both substantial and non-substantial, will be documented in the CSR. Any updates to their respective analyses, study designs, and TFL presentations after this SAP is finalized and approved will be documented in a running Note to the SAP document.

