### 3.2. Secondary Objectives

The secondary objectives of this study are:

- To assess the change in CD8+ TIL density from pre-treatment Transurethral Resection of Bladder Tumor (TURBT) to post-treatment Radical Cystectomy (RC) tissues separately in patients treated with nivolumab or combination of nivolumab/lirilumab.
- To assess percentage (%) change in CD8+ TIL density from pre-treatment TURBT to post-treatment RC tissues separately in patients treated with nivolumab and combination of nivolumab/lirilumab.
- To describe the rate of patients in each cohort who do not get RC within 6 weeks after completion of neoadjuvant treatment specifically and directly related to treatment-related adverse events (AEs).
- To assess the antitumor efficacy of nivolumab and combination of nivolumab/lirilumab as measured by pathologic complete (pT0N0) and partial (<pT2N0) response rate in the two cohorts.
- To assess the rate of recurrence-free survival (RFS) at the two-year time point from the time of registration in patients treated with nivolumab and combination of nivolumab/lirilumab.
- To assess the prognostic and predictive value of the expression of baseline immunohistochemistry (IHC) markers of interest (e.g. PD-1, PD-L1, PD-L2, NKG2D, KIR2DL1/2/3), and change in expression, for pathologic partial and complete tumor response (defined by cystectomy pathologic staging <pT2N0 and pT0N0, respectively), in patients treated with nivolumab and combination of nivolumab/lirilumab.
- To assess the prognostic and predictive value of peripheral blood mononuclear cell (PBMC) T-cell subset status (%CD4+ T-cells, %CD8+ T-cells, %Treg T-cells, %Myeloid Derived Suppressor Cells, %Natural Killer cells, etc.) and change in status, as assessed by flow cytometry analysis, for pathologic partial and complete tumor response (defined by cystectomy pathologic staging < pT2N0 and pT0N0, respectively), in patients treated with nivolumab and combination of nivolumab/lirilumab.

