**7.4.2.5. Proportion of patients who are alive and free of disease in each cohort at 2 years from registration.**

Analytic Plan for this secondary endpoint: Recurrence-free survival (defined as patients who are alive and without evidence of disease recurrence) from the time of registration will be estimated using Kaplan-Meier method for each treatment cohort and compared between the two cohorts using a log-rank test. The two-year disease-free survival estimates and confidence intervals will be provided for each cohort.

**7.4.2.6. The relationship between the expression of baseline IHC markers of interest (e.g. PD-1, PD-L1, PD-L2, NKG2D, KIR2DL1/2/3), and change in expression, for pathologic partial and complete tumor response (defined by cystectomy pathologic staging <pT2N0 and pT0N0, respectively), in patients treated with nivolumab and combination of nivolumab/lirilumab. To also compare the association of study cohort and pathologic response stratified by levels of expression of these biomarkers of interest.**

Analytic Plan for this secondary endpoint: As a general strategy, IHC marker levels in responders vs. non-responders will be compared by a t-test or Wilcoxon rank sum test as appropriate. In addition to evaluating expression on a continuous scale we will explore quantile values for each marker as potential thresholds to discretize the marker levels. The two-year RFS will then be compared between marker groups with a Fisher's exact test as well as via time-to-event analyses using standard methods for survival analysis. Changes in biomarker levels will be computed and compared between groups using a Wilcoxon rank sum test.

**7.4.2.7. The relationship between peripheral blood mononuclear cell (PBMC) T-cell subset status (%CD4+ T-cells, %CD8+ T-cells, %Treg T-cells, %Myeloid Derived Suppressor Cells, %Natural Killer cells, etc.) and change in status, as assessed by flow cytometry analysis, for pathologic partial and complete tumor response (defined by cystectomy pathologic staging < pT2N0 and pT0N0, respectively), in patients treated with nivolumab and combination of nivolumab/lirilumab.**

Analytic Plan for this secondary endpoint: The PBMC T-cell subset status in responders vs. non-responders will be compared by a t-test or Wilcoxon rank sum test as appropriate.

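### SAP section 8 reports no changes, yet the SAP ranks the IHC and PBMC marker analyses above the protocol's tier and omits the interaction test and power caveat that a claim of predictive value needs

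*SAP*

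**What the plan says.** **Status of the SAP.** SAP 2.1 sets the rule: "This SAP supersedes the statistical considerations identified in the protocol; where considerations are substantially different, they will be so identified". SAP section 8, the place set aside for such differences, says in full: "No changes are planned".

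**Protocol.** Section 2.3 places the IHC objective and the PBMC objective ("To assess the prognostic and predictive value of peripheral blood mononuclear cell (PBMC) T-cell subset status") among the exploratory objectives. Section 13.2.4, items 1 and 2, does the same. Section 13.2.4.1 gives the method for the predictive part: "Analyses of the predictive ability of markers will be accomplished via standard tests of treatment-by-marker interaction", using logistic or proportional hazards regression. It closes with a limit: "The study is not powered for these analyses, however, so conclusions regarding the predictive ability of any given marker will be limited".

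**SAP.** Section 3.2 lists both as secondary objectives, with the aim unchanged: "To assess the prognostic and predictive value of the expression of baseline immunohistochemistry (IHC) markers of interest", and likewise for PBMC. Sections 7.4.2.6 and 7.4.2.7 list them as secondary endpoints. For IHC the plan is: "IHC marker levels in responders vs. non-responders will be compared by a t-test or Wilcoxon rank sum test as appropriate". It adds a search of quantile thresholds, two-year RFS by marker group (Fisher's exact test and survival methods) and rank-sum comparisons of marker change. The 7.4.2.6 endpoint also names a comparison of the cohort-response association across marker levels, but its analytic plan assigns no test to that. For PBMC, 7.4.2.7 gives the responder comparison only. Section 7.7.7 borrows the strategy of a SAP section 8.7.5, which does not exist.

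**The concern.** A marker is prognostic if it is associated with outcome whatever the treatment. It is predictive if the treatment effect differs by marker level. Both cohorts receive nivolumab, so the only predictive question this trial could address between its arms is whether the effect of adding lirilumab depends on the marker. A comparison of responders with non-responders does not ask that, and neither does a comparison of RFS between marker groups. Done within one cohort, such a comparison has no comparator. Done on the pooled cohorts, it mixes prognostic and predictive effects.

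A programmer who follows the SAP as the governing document would therefore report secondary results on predictive value from tests that cannot separate the two, after a threshold search in 12 and 24 patients, and without the protocol's warning. A reader who checks section 8 would be told that nothing differs from the protocol.

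**Working it through.** **1. Calibration.** Neither document states a power, alpha or effect size for the marker analyses, so there is no figure of the plan to reproduce for them. For the same 12 + 24 patients, the protocol's exploratory comparison of TIL density (13.2.2.1: 0.80 SD, one-sided 0.1, stated power 82%) gives

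Φ(0.80 × √(3/π) / √(1/12 + 1/24) − 1.2816) = Φ(2.211 − 1.282) = 82.4%.

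The maximum 90% exact interval widths come to 0.509 and 0.361 (stated 0.51 and 0.36). These figures reproduce.

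**2. The texts side by side.**

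| Item | Protocol | SAP |
|---|---|---|
| Tier of IHC and PBMC markers | Exploratory (2.3, 13.2.4) | Secondary (3.2, 7.4.2.6, 7.4.2.7) |
| Predictive aim | Stated | Stated |
| Interaction test | Yes (13.2.4.1) | Absent throughout |
| Not-powered statement | Yes (13.2.4.1) | Absent throughout |
| RFS estimates | "One-year and two-year disease-free survival estimates and confidence intervals will be provided for each cohort" (13.2.3.1) | Two-year only (7.4.2.5, 7.7.4) |
| Interim boundary | 3 or more of 6 in a single cohort, cohorts monitored separately (5.4, 13.1.1) | 3 in the first 6, 6 of 12, then 9 of 18 pooled over cohorts (7.8) |
| Declared in SAP section 8 | n/a | None |

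**3. Does the specified test separate prognostic from predictive?** Simulation of 36 patients (12/24), 4,000 runs per setting. Assumptions, none of which come from the documents: standard normal marker, logistic response model with about 35% response at the marker mean, two-sided 0.05, pooled rank-sum test of responders against non-responders.

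- No marker effect: rejects in 4.9% of runs.
- Purely prognostic, same odds ratio of 2, 3 or 4 per SD in both cohorts: rejects in 42%, 75% and 90%.
- Purely predictive, effect in Cohort 2 only, odds ratio 2, 3, 4 or 6 per SD: rejects in 20%, 40%, 52% and 65%.

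A prognostic-only odds ratio of 2 (42%) and a predictive-only odds ratio of 3 (40%) give nearly the same rejection rate. A significant result therefore does not say which is present.

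**4. What would the protocol's interaction test deliver?** Split the marker at the median (6 + 6 in Cohort 1, 12 + 12 in Cohort 2). With d the log ratio of odds ratios, the variance is the sum of 1/[n p(1−p)] over the four cells, and power is Φ(d/SE − 1.96).

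- Response 50% in marker-positive Cohort 2 and 30% elsewhere: d = ln 2.33 = 0.847, SE = √(0.333 + 0.397 + 2 × 0.794) = 1.52, power 8%.
- 60% and 70% in that cell: ratios 3.5 and 5.4, power 13% and 19%.
- 70% against 20% within Cohort 2, with 30% in both Cohort 1 cells: ratio 9.3, SE 1.58, power 29%.
- Ratio needed for 80% power: exp(2.80 × 1.543) ≈ 75 with rates near 30%; exp(2.80 × 1.414) ≈ 53 with rates near 50%.

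In the simulation, the likelihood-ratio interaction test with the marker kept continuous rejected in 9% to 11% of runs without any interaction, against a nominal 5%. The protocol's caveat is justified by the numbers.

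**5. Multiplicity, as an illustration only.** Count PD-1 and PD-L1 (the IHC stains that protocol 14.1.4 commits to) and the five named PBMC subsets, each at baseline and as change, for two response definitions: 2 × 2 × 2 + 5 × 2 × 2 = 28 tests. At an assumed 0.05 level, 28 × 0.05 = 1.4 false positives are expected. If the tests were independent, 1 − 0.95^28 = 76% is the chance of at least one.

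**The case against.** **Version.** The SAP history says it was updated to agree with protocol V3.0 of 10 December 2019. The supplied protocol appears to be another version: it allows 10 weeks from TURBT where the SAP allows 8, and it admits patients who refuse cisplatin, whom the SAP does not mention. A reader might infer that the SAP promoted the markers, dropped the test and hid this behind section 8. The documents do not support that. V3.0 is not available, section 8 may have been true when written, and the protocol may have moved later. This objection stands as to cause. It does not remove the conflict between the two texts now in force.

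**Disclosure elsewhere.** The SAP history does record the removal of the one-year RFS analysis and the addition of the interim section. That is fair, but it logs changes between SAP drafts, does not present them as departures from the protocol, and is silent on the marker tier, the interaction test and the caveat.

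**Breadth of the SAP plan.** A reader might also infer that the SAP offers only responder comparisons. It offers more for IHC, including RFS by marker group and the stratified cohort-response comparison, and 7.7.7 seems meant to extend that strategy to PBMC. The stratified comparison does address the predictive question, but without an assigned test. The other analyses do not address it.

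**Multiplicity.** Counting every named marker would give 48 tests, 2.4 expected false positives and 91%. The documents do not support that count as a finding. The marker lists are open-ended, KIR staining depends on resources (protocol 14.1.5), no alpha is set for these tests, and complete response is nested in response below pT2N0, so independence fails. The same tests are in the protocol's exploratory plan, so relabelling would not reduce the count.

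**Consequence.** The primary endpoint is safety and the key secondary endpoint is CD8+ density. Neither document has an alpha hierarchy that the secondary label would enter. This limits the harm to how the marker results are labelled and read.

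**Conclusion.** The concern holds as a mismatch between the current SAP and the supplied protocol that SAP section 8 does not disclose. The marker analyses rank higher in the SAP, keep a predictive aim, and lack both the method that could address it and the statement that limits it. What the SAP specifies can support at most a prognostic claim.

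The comparison of texts needs no assumptions. The sizes do: rejection in 42% to 90% of runs for a purely prognostic marker, and interaction power of 8% to 29%, rest on the assumed response rates and effect sizes shown. Restoring the interaction test would match method to objective but would not make it informative. Power is very low, and the cohorts are sequential and not randomised, so treatment is confounded with calendar time. The primary and key secondary analyses are unaffected by the marker issue.

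**What to change.** - Return SAP 7.4.2.6, 7.4.2.7 and the matching bullets of 3.2 to exploratory.
- Either restore the interaction test from protocol 13.2.4.1 together with its not-powered statement, adding that sequential non-randomised cohorts confound treatment with time, or delete the word predictive from these objectives. If the stratified cohort-response comparison stays for IHC, assign it a method.
- Correct the reference to SAP section 8.7.5 in 7.7.7; the preceding marker section, 7.7.6, seems to be intended.
- Replace the statement in section 8 with the actual differences from the protocol version in force. These include at least the marker tier, the interaction test and caveat (whichever remain different), the one-year RFS estimate, and the 6-of-12 and pooled 9-of-18 interim boundaries. Those boundaries must also be reconciled with the protocol's per-cohort rule.

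The cost is SAP wording and, if the test is restored, one interaction model per marker and endpoint. No data collection or sample size changes. The marker results carry a weaker label, which is the label the protocol already gives them.

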## **9. REPORTING CONVENTIONS**

The mean and median will be displayed to one decimal place greater than the original value and the standard deviation will be displayed to two decimal places greater than the original value. All statistical programming and analyses will be performed using SAS® Release 9.4 (SAS Institute Inc., Cary, North Carolina, USA).

The following standards will be used in the data presentation:

- Section 14 tables should be in landscape format. Output should adhere to US / International Conference on Harmonization (ICH) margins and should not require changes for European page size. For item 14 tables, a blank row will separate the header from the content of the table listing. For tables that have “n (%)”, the placement should be centered below “N=xx” in the column header. Frequency tables will be center justified. Descriptive statistics will be decimal aligned.

- Percentages presented in in-text tables should be rounded to one decimal using the SAS rounding function. If “%” is part of the column heading, do not repeat the “%” sign in the body of the table. Unless specified otherwise, “%” should reflect the total population of the treatment groups. Any deviation from that should be part of the footnote. For 0 counts, leave the corresponding percentage blank.
- The format for minimum and maximum should be “Min, Max”. SD should be the default for representing scale, unless standard error has been specified. Standard deviation should be abbreviated as “SD”, and presented next to the mean value, without any +/- sign. The SD should have one additional decimal place beyond that of the mean (e.g. mean has one decimal place, SD should have two).
- “N” will represent the entire treatment group for the population group being analyzed, while “n” will represent a subset of the treatment group. For tables with population designated as a row heading, “N” should be used (i.e. tables where all participant data is not available for every variable within a treatment group). As a guideline, if the number is used in a denominator it should be presented as “N”. If the number is used in the numerator, it should be presented as an “n”.
- The heading should consist of four lines. Line 1: Sponsor identifier. Line 2: Protocol identifier. Line 3: blank line. Line 4: Table/Appendix number Table Title – Population. The title for in-text tables should begin with the Table/Appendix number.
- All data listings will be sorted by Patient Number and time point (if applicable).
- The date format for all dates is DDMMMYYYY.

A solid line should appear both above and below the column headings of a table. A solid line should appear at the end of the table or at the bottom of each page if the table extends to more than one page. Footnotes should start after the bottom solid line.

